We will recruit BHTs from agencies whose leadership have agreed to allow BHTs to participate in this project. Research staff will contact leadership at community agencies with an overview of the study and confirm a plan to distribute information about the study in the following ways 1) leaders will email their team describing the study and inviting them to participate and/or, 2) agency leaders and participating BHT's will share BHT emails with research staff who will email BHT's directly to invite them to participate. The email will contain an electronic link to an electronic consent to be contacted form in REDCap.

After BHTs consent to participate in the trial, we will randomize them in pairs to one of the two study arms. Members of the research team will teach BHTs how to use the app during a brief individual meeting that will occur at the school where the BHT works, at their agency, or remotely, depending on BHTs' preference and possible COVID-19 restrictions. BHTs also will complete baseline questionnaires on REDCap on their demographic information, intentions to collect data, and the determinants of intention: attitudes, norms, and self-efficacy. BHTs will be compensated \$25 for these baseline activities, which we anticipate will take approximately 30-60 minutes.

We then will ask BHTs to use their assigned app to collect data daily for 3 weeks, or up to 15 sessions. All data collection will occur via the BHT's smartphone, or if preferred, through the research team's iPad. The Mozzaz app and associated server is HIPAA compliant. BHTs will only record de-identified data in the mobile app; neither the app nor study staff will collect identifiable information about the students with whom the BHTs work. As originally written, this project included research staff conducting in-person observations of BHTs' use of the app to verify BHTs' self-report data. Given COVID-19 restrictions, we propose multiple options to replace in-person observations:

1. *In the event that the BHT is working in person and in-person observation is possible:* Research staff will coordinate with the BHT to facilitate in-person observations over the course of approximately three weeks. Research staff would complete up to observations over the course of approximately three weeks (each up to two hours long.)

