2. *In the event that the BHT is working in person but in-person observation is not possible:* In lieu of in-person observations, research staff will administer weekly one-hour interviews with the BHT about their experience using the app. Research staff would complete up to three one-hour interviews over the course of approximately three weeks.
3. *In the event that the BHT is working remotely:* Research staff will coordinate with the BHT to facilitate remote observations through their video conferencing platform. Research staff would complete up to three one-hour observations over the course of approximately three weeks.

In each scenario, BHTs will be compensated \$25/hour per observation or interview (up to six hours, up to \$150) and \$10 per ten-minute follow-up questionnaire (\$20).

After the three-week trial period concludes, BHTs will return their iPad to the study team if they were loaned one. Participants will complete ten-minute questionnaires about perceptions of app usability, their intentions to collect data, and determinants of their intentions to collect data (attitudes, norms, and self-efficacy) via REDCap. We also invite all participants to participate in an additional qualitative phone interview to probe deeper into the user experience and intentions to collect data. This optional interview will take about 30 to 60 minutes and BHTs will be compensated \$25 for completion.

In total, participants will be compensated up to \$220 for their participation in the study. Specifically, they will be paid:

- \$25 for the initial training and baseline questionnaires (about 30-60 minutes)
- \$25 for each set of observations or interviews (up to six hours, up to \$150)
- \$10 for two ~10 minute follow-up questionnaires (\$20)
- \$25 for qualitative interview about experience using the app (30-60 minutes)

Timeline	Measures
Baseline	
 • Demographic questionnaire • Intentions and determinants questionnaire
Trial Period	Mobile application analytics
Post-Trial Period	
 • Intentions and determinants questionnaire • System Usability Scale (SUS) • ASSISTS app feedback form 
 ○ Basic app arm ○ Behavioral economics-informed app arm • Post-trial qualitative interview guide

ANALYSIS PLAN

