There are three data collection quality metrics of interest: data collection consistency, timeliness, and completeness. Consistency was the percentage of intervals in which aides entered data per session. Timeliness was the delta (time difference in minutes) between behavior occurrences and the aides' data entry related to those behavior occurrences. Completeness was the percentage of metrics such as frequency, duration, severity, or accuracy that aides logged on behavior form entries out of the total number of metrics for that behavior. These metrics were captured via web analytics in partnership with our digital health company. The research team will also conduct two ten-minute follow-up questionnaires with BHTs.

The secondary outcomes of interest are: 1) the change in intentions to collect data and the determinants of intention (attitudes, norms, and self-efficacy), and 2) the usability of the app. We will calculate the change in intentions and determinants of intention by comparing the questionnaires distributed at baseline and after the trial. We will assess usability using the System Usability Scale (SUS) post-observation and by conducting qualitative interviews.

We will analyze outcomes as continuous variables at the BHT level across time points. Initially,

all outcomes will be described and compared between groups using summary statistics (means, medians, and estimates of variance). For each measure, the analysis data set will contain one

observation with each participant's outcome measure at baseline and post-trial. To determine the preliminary efficacy of our implementation strategy, the behavioral economics enhanced app, we will compare the two study arms (basic app vs. enhanced app) on the primary outcome (proportion of time intervals BHTs take data) and the secondary measures (change in intentions to collect data and the determinants of intention [attitudes, norms, and self-efficacy], and app usability), using linear regression with random effects for BHT and time (baseline, post-trial period). The regression will include treatment arm, time (baseline and endpoint), and the interaction between group and time. The coefficient associated with the interaction will indicate the effect of one treatment arm versus the other on data collection.

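### For the four questionnaire scales, arm × time is a difference in mean change; adjusting for the baseline already collected is usually more precise, and the random time term should go

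*Combined protocol and SAP*

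**What the plan says.** The timeline table at the end of PROCEDURES lists the intentions and determinants questionnaire at baseline and again post-trial. This gives four scales with two scores per behavioral health technician (BHT): intentions, attitudes, norms and self-efficacy. The ANALYSIS PLAN defines the outcome as change: "We will calculate the change in intentions and determinants of intention by comparing the questionnaires distributed at baseline and after the trial".

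One model is assigned to the primary outcome and all secondary measures, "using linear regression with random effects for BHT and time (baseline, post-trial period", with fixed terms for arm, time and arm × time. The interaction is the effect: "The coefficient associated with the interaction will indicate the effect of one treatment arm versus the other on data collection". No baseline covariate appears anywhere. The same section describes the analysis data set as a single "observation with each participant's outcome measure at baseline and post-trial".

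PROCEDURES adds two relevant facts:

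- Allocation: "After BHTs consent to participate in the trial, we will randomize them in pairs to one of the two study arms". No matching factor is named.
- Timing: app training is described next, and then "BHTs also will complete baseline questionnaires on REDCap on their demographic information, intentions to collect data". Payment covers both together, "for the initial training and baseline questionnaires (about 30-60 minutes". The order of training and questionnaire is not given.

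Usability is measured once: "We will assess usability using the System Usability Scale (SUS) post-observation".

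**The concern.** With two time points the interaction subtracts each person's whole baseline score from the post-trial score. That is the best use of the baseline only when the regression slope of post-trial on baseline is 1. At low or moderate correlation the slope is smaller, and the subtraction adds baseline noise. With equal SDs and a correlation below 0.5, the result is less precise than ignoring the baseline altogether. Thirty participants leave little precision to spare, and the closing paragraph of the ANALYSIS PLAN says the results will support a publication and a grant application for a larger trial. No bias is alleged.

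Two wording problems sit in the same paragraph. The description of the data set can be read as one row holding both scores, which suits baseline adjustment, whereas a random effect for BHT needs two rows. And a random effect for a two-level time factor is redundant or not identified under most readings.

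**Working it through.** The plan gives no SD, correlation, effect size or power for these scales, so there is no stated figure to reproduce.

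**Inputs.** From the documents: 30 BHTs, two arms, randomised in pairs. Assumed: 15 completers per arm, baseline SD 1, post-trial SD *k*, baseline/post-trial correlation ρ from 0.3 to 0.9.

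**Step 1: what the interaction is.** In a simulated complete data set, the random-intercept model gave an arm × time coefficient of −0.1562 (SE 0.3647). Regressing the change score on arm gave the same estimate and SE. Adding baseline gave an arm coefficient of −0.3650 whether the response was the post-trial score or the change.

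**Step 2: variances.**

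- Change: (1 + k² − 2ρk)(2/15).
- Baseline-adjusted: k²(1 − ρ²)(2/15)f, where f is the small-sample cost of estimating the slope. Unpaired, f = 1 + 1/(30 − 4) = 27/26. On 15 pair differences, f = 1 + 1/(15 − 3) = 13/12.

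Example at k = 1, ρ = 0.5, unpaired: 0.75 × 27/26 ÷ 1 = 0.779.

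Adjusted/change variance ratio (below 1 favours adjustment):

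| Setting | ρ 0.3 | 0.5 | 0.7 | 0.8 | 0.9 | Change better when |
|---|---|---|---|---|---|---|
| Equal SDs | 0.675 | 0.779 | 0.883 | 0.935 | 0.987 | ρ > 0.926 |
| Post-trial SD 10% larger | 0.738 | 0.849 | 0.956 | 1.005 | 1.038 | ρ 0.79–0.96 |
| Post-trial SD 25% larger | 0.815 | 0.927 | 1.018 | 1.038 | 0.987 | ρ 0.65–0.89 |
| Post-trial SD 10% smaller | 0.603 | 0.693 | 0.780 | 0.818 | 0.841 | never |
| Equal SDs, pairs modelled | 0.704 | 0.813 | 0.921 | 0.975 | 1.029 | ρ > 0.846 |

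At k = 1 the ratio is ((1 + ρ)/2)f, which gives the break-evens 0.926 and 0.846. On interval width they are 0.920 and 0.820, because one residual df is lost. Simulation of 40,000 trials per setting gave 0.67, 0.78 and 0.88 at ρ 0.3, 0.5 and 0.7 (equal SDs, unpaired), with 95% coverage.

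**Step 3: interval half-widths.** Equal SDs, SD units; t = 2.048 (28 df) and 2.052 (27 df) unpaired. At ρ = 0.5: 2.048 × √(2/15) = 0.75, against 2.052 × √(0.75 × 27/26 × 2/15) = 0.66.

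| ρ | Unpaired: change → adjusted | Pairs modelled: change → adjusted |
|---|---|---|
| 0.3 | 0.89 → 0.73 | 0.93 → 0.78 |
| 0.5 | 0.75 → 0.66 | 0.78 → 0.71 |
| 0.7 | 0.58 → 0.55 | 0.61 → 0.59 |

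**Step 4: largest loss.** Adjustment does worst when the true slope is 1. The SE then rises by √f − 1, which is 1.9% unpaired and 4.1% with pairs.

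**Step 5: missing scores.** These are simulations with equal SDs and 15,000 replicates.

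- Three of 15 post-trial scores missing at random per arm: adjusted analysis of those with a post-trial score against the likelihood-based arm × time model that keeps everyone, ratio 0.73, 0.82 and 0.91 at ρ 0.3, 0.5 and 0.7.
- Three of 30 baselines missing at random, filled with the pooled baseline mean: variance 0.62, 0.74 and 0.87 of planned arm × time, and 0.90, 0.93 and 0.98 of complete-case adjustment; coverage 0.950 to 0.952.

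**Step 6: random time.** Two time points supply three covariance elements. A BHT intercept plus residual is identified (rank 2 of 2). A correlated slope is not (3 of 4), nor is BHT-by-time (2 of 3), nor an independent slope coded −0.5/+0.5 (2 of 3). An independent slope coded 0/1 is identified (3 of 3), but it forces the post-trial variance to be at least the baseline variance. As a two-level factor, random time duplicates fixed time. With complete data none of these changes the arm estimate.

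**Step 7: outcomes without a baseline.** For the app metrics and the usability scale only post-randomisation rows exist. The fixed-effect design then has rank 2 of 4, so arm × time cannot be estimated.

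**The case against.** The best defence is that outcome and analysis agree. The plan defines the outcome as change, and arm × time estimates the difference in mean change without bias. These are secondary outcomes in a preliminary trial, and the gain depends on a correlation the documents do not give. Over three weeks the same self-report scale might correlate highly: at ρ = 0.8 with equal SDs the half-width falls only from 0.473 to 0.458. If pairs are modelled and the post-trial SD is 10% or 25% larger, change is better for ρ of about 0.70–0.97 or 0.56–0.92.

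The loss ceilings also have limits. The 1.9% assumes all 30 complete; with 24 it is √(1 + 1/20) − 1 = 2.5%, and with 20 it is 3.1%. With pairs, the loss in interval width is 4.8%. Under dropout the advantage is shown for ρ 0.3–0.7; at ρ = 0.9 the ratio is about 1.00 with equal SDs and 1.04 with the post-trial SD 10% larger.

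All of this stands, and it makes the point one of efficiency. It does not reverse the advice: the possible loss is a few per cent of the SE, while the possible gain at moderate correlation is much larger. Nor is the stated outcome lost, because the adjusted arm coefficient is the same for change as for the post-trial score.

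It is also fair to say that the quoted sentence speaks of data collection, the primary outcome, for which non-estimability is the larger problem. The same model is nevertheless assigned to the four scales. The reading of the data-layout sentence is secondary, and the point does not depend on it.

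**Conclusion.** The point holds. For the four scales with a baseline, the planned contrast is valid but usually less precise than adjustment, with 12% to 32.5% excess variance removed at ρ 0.3–0.7. That range assumes equal SDs, 15 completers per arm and an unpaired analysis. The benefit is small or slightly negative at high correlation or with more variable post-trial scores. This is an improvement the plan should make, not a threat to validity.

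The absence of bias requires a baseline answered before exposure to the assigned app, which the plan does not secure. If the app shifted the baseline by *d*, the change contrast would be biased by −d and the adjusted contrast by about −ρd (equal SDs). The ordering therefore matters to both analyses, and less to the adjusted one.

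**What to change.** For intentions, attitudes, norms and self-efficacy only, specify one analysis in advance:

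- Regress the post-trial score on arm and the same scale's baseline score, one row per BHT, with no random time and no arm × time term. Report the adjusted arm difference with its 95% CI.
- Include every BHT with a post-trial score. Fill a missing baseline with the baseline mean pooled over both arms, and fix this rule now.
- Leave pairs out of the main model, since no matching factor is named, and give one sensitivity analysis with pair as a fixed effect. If pairs or strata are formed on a named factor, put that factor in the main model.
- State that the baseline questionnaire is completed before the BHT sees the assigned app.

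For the primary outcome and the usability scale, replace arm × time with a post-randomisation comparison of arms.

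The cost is plan wording, one residual df (28 to 27) and a label that becomes a baseline-adjusted post-trial difference. BHTs without a post-trial score drop out. Leaving pairs out is conservative if pair members resemble each other: at ρ = 0.5 and an assumed pair ICC of 0.2, the simulated half-width is 0.65 with 97% coverage, against 0.62 with 95% if pairs are modelled. At ICC 0 it is 0.66 against 0.70. No new data are needed.
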